 - Infection (wound infection or systemic infection) during the observation period.
- After consultation patients can be withdrawn due to withdrawal of informed consent to participate in the study at the patients' own request at any time for any reason.

Population

Study group: The "Hvidovre population":

We will include patients undergoing laparoscopic hemicolectomy for cancer scheduled for anesthesia with total intravenous anesthesia combined with epidural anesthesia on Hvidovre Hospital according to the intervention described above.

Eligibility criteria:

Inclusion criteria:

1. Patients over 18 years
2. Patients diagnosed with colorectal cancer (UICC stadium I-III) and scheduled for laparoscopic hemicolectomy.
3. ASA class I-III (Classification of the American Society of Anesthesiology)

4. Patients scheduled for anesthesia with propofol, remifentanil and epidural anesthesia.
5. Signed informed consent

Exclusion criteria:

1. Known immune-defects
2. Patients undergoing neoadjuvant chemo or radiotherapy
3. History of previous cancer
4. Patients in immunomodulatory treatment within last 6 months
5. Daily oral or intravenous steroid-use
6. Patients that have undergone major surgery within one month before planned colon resection.

Control group: The “Zealand University Hospital population”

The immunological and oxidative stress in relation to abdominal surgery (IMOX) study is ongoing at Zealand University Hospital, Roskilde. It is a prospective explorative study cohort that consists of 60 patients undergoing laparoscopic colorectal cancer surgery. The aim of the study is to characterize the immunological and oxidative stress response to surgery. Outcomes similar to the primary and secondary outcomes of the ANIMOX-study are included in the IMOX-study. Patients are already included in the IMOX-study and blood samples are collected and kept in a bio bank.

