We will retrieve data on our main outcomes from the IMOX study in our analysis. Only electronic data will be used and no biologic material will be transferred from the IMOX project to ANIMOX. The population will be stratified according to anesthetic technique, which, according to the standard operating procedure, is either total intravenous anesthesia with propofol and remifentanil or volatile anesthesia with sevoflurane combined with a fast acting opioid (remifentanil or sufentanil). Patients anaesthetized with other techniques including epidural or other regional blocks will be excluded from the analysis.

Biological samples

To characterize the immunological response to surgery we obtain blood samples for analysis on postoperative day -1, 1, 2, 3 and 10 (or at the visit on day 10-14 where pathology results are given).

Handling of blood samples

Blood samples will be drawn by a trained professional and analyzed immediately at the standard lab facilities at Hvidovre Hospital and destroyed immediately hereafter. The results will be accessible in Sundhedsplatformen.

Primary outcome:

The primary outcome will be changes in neutrophil to lymphocyte ratio from day 0 to day 1. Neutrophil to lymphocyte ratio has been linked to poor outcome after colorectal cancer surgery. The ratio will be estimated using absolute numbers from differential counts pre and postoperatively.

Blood samples

Standard blood samples will be obtained and analyzed immediately at each time point. These include Hgb, Leucocytes including a differential count, thrombocytes, ALAT, LDH, Alkaline phosphatase, bilirubin, INR, albumin, Na, K, Creatinine, CRP and Glucose.

Quality of Recovery – 15 questionnaire

At each time point (day -1, 1,2 and 10) the patients are asked to fill in the validated Quality of Recovery Questionnaire QoR-15²⁷. The QoR-15 questionnaire results in a score of 0–150. These outcome measures will be correlated with changes in immunologic outcome measures in the perioperative period.

Guidelines for oral and written consent and participant timeline

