Data from the Hvidovre population and the Zealand University Hospital population will be combined to evaluate the effects of inhalational anesthesia (sevoflurane and opioid), total intravenous anesthesia (propofol and remifentanyl) and total intravenous anesthesia (propofol and remifentanyl) combined with epidural anesthesia (bupivacaine with opioid). Only electronic data will be used from the IMOX project – no biologic material will be transferred.

Baseline and clinical characteristics for patients, stratified for anesthesia type will be presented as frequencies for nominal, dichotomous and ordinal variables and medians with IQR for continuous variables. Outcome variables will be presented and described with appropriate tests. Depending on whether data is normally distributed or not, differences between the groups will be assessed using parametric or non-parametric statistics, respectively.

Risks, harms and inconveniences

Patients will receive the standard care at the respective hospital. The study does not influence any treatment or intervention related to the hospitalization.

Peripheral blood samples

Blood will be drawn from puncture of the cubic vein. The needle can cause minor discomfort including hematoma, which will disappear within few days.

QoR-15 questionnaires

Filling in the QoR-15 questionnaire will require a short amount of time and effort at the four time points.

Ethical considerations

Research within this field is until now very limited, but optimization of the anesthetic technique used for cancer surgery can benefit millions of people undergoing surgery for cancer in the future.

Approval from the regional scientific ethical committee is mandatory. Important modifications in the protocol will be communicated to the committee and approved before implementation.

Written consent from all participants will be obtained before inclusion as described above. Participants can at any time withdraw their consent.

All personal information about enrolled patients will be collected and protected according to Danish Law to ensure confidentiality before, during and after the study.

Data will only be assessed by participants of the study group according to the approval from the Danish Data Protection Agency.

Risk of random findings

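### Two non-randomised hospital cohorts are pooled to evaluate anesthetic effects with no case-mix adjustment, and both epidural contrasts are completely confounded with hospital

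*Combined protocol and SAP*

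**What the plan says.** The Design and approvals section describes a prospective cohort study; nobody is randomised to a technique.

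- **Study group (Population section).** "We will include patients undergoing laparoscopic hemicolectomy for cancer scheduled for anesthesia with total intravenous anesthesia combined with epidural anesthesia", all at Hvidovre Hospital.
- **Control group (Population section).** Of IMOX, at Zealand University Hospital, the protocol says: "It is a prospective explorative study cohort that consists of 60 patients undergoing laparoscopic colorectal cancer surgery". These patients are grouped as TIVA or sevoflurane. The section adds: "Patients anaesthetized with other techniques including epidural or other regional blocks will be excluded from the analysis". On what is transferred: "We will retrieve data on our main outcomes from the IMOX study in our analysis".
- **Primary outcome.** "The primary outcome will be changes in neutrophil to lymphocyte ratio from day 0 to day 1".
- **Data analysis.** The stated purpose is causal in wording: "Data from the Hvidovre population and the Zealand University Hospital population will be combined to evaluate the effects of inhalational anesthesia", TIVA, and TIVA with epidural. Patient characteristics are tabulated: "Baseline and clinical characteristics for patients, stratified for anesthesia type will be presented as frequencies for nominal, dichotomous and ordinal variables". The comparison itself is: "differences between the groups will be assessed using parametric or non-parametric statistics, respectively", depending on normality.

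No covariate, regression, matching, weighting or sensitivity analysis is named. No sentence limits what may be concluded from a comparison across the two hospitals.

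**The concern.** In a non-randomised comparison, a difference in NLR change between groups can come from the anesthetic, from the kind of patient in each group, or from anything else that differs between hospitals. A baseline table displays imbalance but does nothing about it, and the choice between a parametric and a non-parametric test does not bear on it.

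There are two separate problems. Case mix can be handled in part, by adjustment for measured covariates, and the plan names none. Hospital cannot be handled at all for the epidural contrasts, because no analysed patient had an epidural at Zealand and the Hvidovre study group is defined by having one. The plan acknowledges neither problem, so a p-value below 0.05 for the epidural group could be reported as an epidural effect when the data cannot show that.

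**Working it through.** **1. The plan's own figure.** The Study size section gives a mean rise of 5.33 (SD 3.33), a 50% smaller rise as the target, power 0.8 and alpha 0.05. The target difference is 0.5 × 5.33 = 2.665. For two equal groups, n = 2 × [3.33 × (1.960 + 0.842) / 2.665]² = 24.5, rounded up to 25 per group. The stated 25 reproduces. It is the size for an unadjusted, unconfounded two-group comparison.

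**2. Technique by hospital, from the Population section.**

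| Technique | Hvidovre | Zealand (IMOX) |
|---|---|---|
| TIVA + epidural | 30 (evaluable target) | 0 (excluded) |
| TIVA | 0 | part of up to 60 |
| Sevoflurane | 0 | rest of up to 60 |

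The TIVA/sevoflurane split is not given.

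**3. Estimability.** Take columns for intercept, TIVA, sevoflurane and Hvidovre. Every patient who is neither TIVA nor sevoflurane is at Hvidovre, so Hvidovre = intercept − TIVA − sevoflurane. Four columns have rank 3, whatever the split (confirmed numerically at 30/30/30 and 30/15/45). Neither epidural contrast can be estimated apart from hospital. TIVA versus sevoflurane can, because both groups are at Zealand.

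**4. Illustration of the consequence.** Assume no anesthetic effect, SD 3.33 in both groups, a two-sided t-test at 0.05, and a non-anesthetic difference δ in NLR change. With SE = 3.33 × √(1/30 + 1/n), the chance of p<0.05 comes from the noncentral t distribution with 28 + n degrees of freedom and noncentrality δ/SE. The values of δ and n are assumptions. Relative to the planned difference, 1.0/2.665 = 38% and 1.5/2.665 = 56%.

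| Comparator n | SE | δ = 1.0 | δ = 1.5 |
|---|---|---|---|
| 15 | 1.053 | 15% | 29% |
| 30 | 0.860 | 21% | 40% |
| 45 | 0.785 | 24% | 47% |
| 60 | 0.745 | 26% | 51% |

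The last row is the literal comparison in the Study size section, Hvidovre against all of IMOX. With δ = 0, each row is 5%.

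**5. What adjustment can and cannot do.** A simulation at 30/30/30 used age, sex, ASA class, stage and procedure (5,000 replicates; all except sex differing by an assumed 0.5 SD between hospitals; δ = 1.0). Rejection was 19–21% unadjusted. Adjusted, it was 5%, 9% and 17% when the covariates explained all, half and none of the difference. The remaining bias was about 0, 0.5 and 1.0 unit. The unexplained part stays in full.

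**The case against.** The strongest reply is that the plan is modest. It calls itself exploratory, declares a cohort design reported under STROBE, and in the introduction aims to characterise differences. The outcome is a change score, which takes some account of a patient's starting NLR. All of this is fair and softens the causal reading. It does not supply an adjustment plan, it does not remove hospital or case-mix differences in the rise itself, and the analysis section still speaks of effects and sets p<0.05.

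A second reply is that nothing here shows the hospitals differ. That stands. The rejection rates in the working rest on assumed differences and group sizes; only the rank result is documented fact.

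Three stronger readings are tempting and are not supported:

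- **That dexamethasone use differs.** The Intervention section withholds it at Hvidovre because it might affect the immune response. IMOX practice is not described, so a difference is possible but not shown. The same holds for case mix: Hvidovre takes hemicolectomy with listed exclusions, and IMOX is described only as colorectal cancer surgery.
- **That withdrawal is one-sided.** The Hvidovre evaluable target leaves out patients who meet withdrawal criteria, some of which concern events after day 1. The criteria are permissive, the analysis section defines no analysis set, and IMOX rules are not documented.
- **That adjustment would make the epidural contrasts causal.** It cannot; step 3 rules that out.

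**Conclusion.** The concern holds in this form: the pooled comparison names no adjustment for case mix, and both epidural contrasts are completely aliased with hospital, without any text limiting the conclusion. The aliasing is exact and needs no assumption beyond the stated group definitions. The size of any resulting error is unknown. The 15–26% for a 1.0-unit difference shows sensitivity under assumed inputs and is not an estimate for this study.

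A reader might infer that the whole comparison is uninformative. The documents do not support that. TIVA versus sevoflurane lies within one hospital, though it is still non-randomised and unadjusted as planned. The epidural contrasts can be reported as the combined difference of epidural and hospital.

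**What to change.** 1. **State the limit.** Say in the Data analysis section and in the conclusions that Hvidovre-versus-Zealand contrasts estimate epidural and hospital together and cannot be attributed to epidural alone.
2. **Align the cohorts.** Restrict IMOX to patients who meet the Hvidovre eligibility criteria that can be applied, including hemicolectomy, so that procedures overlap between hospitals.
3. **Name the model.** Analyse NLR change to day 1 with a linear model containing anesthesia group, age, sex, ASA class and stage, fixed before IMOX outcome data are seen. Report estimates with 95% confidence intervals. Add preoperative NLR as a sensitivity analysis, because change-score and baseline-adjusted analyses rest on different untestable assumptions when groups are not randomised.
4. **Widen the IMOX request.** Ask for these covariates and perioperative dexamethasone use. If dexamethasone varies within IMOX, adjust for it in TIVA versus sevoflurane, and repeat the epidural contrasts using only IMOX patients who did not receive it. If it does not vary, report it as part of the hospital difference.
5. **Check the analysis set.** As a sensitivity analysis, include every consenting Hvidovre patient with a day-1 value, whatever complications follow.

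**Cost.** This needs SAP wording and a longer data extract; the Hvidovre covariates are already collected at screening or after inclusion. Precision falls. In the simulated model, which also carried a procedure term, the variance of epidural versus TIVA at 30/30/30 grew by 1.08, 1.23 and 1.66 when age, ASA, stage and procedure each differed by an assumed 0, 0.5 and 1.0 SD between hospitals. If the covariates predict nothing, power for 2.665 units falls from 87% to 84%, 80% and 65%. At 30/15/15 it falls from 70% to 64%, 59% and 46%. The list must therefore stay short. Restricting IMOX also reduces the comparators, and none of this removes the hospital effect.

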This study, initiated by Center for Surgical Science, Zealand University Hospital, will be a prospective cohort study. Approval from Danish Data Protection Agency and the Regional Committee for Health Research and Ethics is required. The study will require informed consent from participants.

Permission to transfer data from the IMOX study will be obtained from the Danish Data Protection Agency. The trial protocol will be submitted to clinicaltrials.org before initiation of the trial. Manuscripts will be prepared according to the STROBE statement²⁵.

Study setting

The study will take place at Hvidovre Hospital. This is a Danish university hospital. It supports 500,000 people and is one of four main emergency hospitals in Copenhagen Denmark. About 300 laparoscopic colon resections are performed at this facility every year.

Intervention

Participants will undergo laparoscopic colon resection for cancer. They will be anaesthetized according to the standard operating procedure at Hvidovre Hospital (see appendix 1) with the exception that no dexamethasone is administered as it could modulate the immune response. This includes anesthesia induction and maintenance with intravenous propofol and remifentanyl. Patients will receive 4 mg ondansetron at the end of anesthesia.

A thoracic epidural catheter will be installed preoperatively and kept for up to three days. After an initial bolus with bupivacaine, continuous infusion of bupivacaine and sufentanyl will be used to maintain the epidural analgesic effect. Postoperatively the epidural will be paused or discontinued if it is displaced or if side effects occur. It will only be re-installed if there is still need of neuraxial analgesia.

Patients will follow a standard Enhanced Recovery After Surgery (ERAS) protocol used at the facility.

Blood samples will be obtained before surgery and at four time points postoperatively and patient files will be assessed for adverse events within 30 days from surgery.

Withdrawal criteria:

Patients can be withdrawn from the study for any of the following reasons:

- Failure to adhere to the anesthesia intervention described above- including failure to install effective continuous epidural anesthesia.
- Adverse events after surgery
 - Any complication over grade 2 in Clavien-Dindo²⁶ classification
 - Blood transfusion
 - Deep vein thrombosis or pulmonary embolism
 - Anastomotic leak
 - Acute renal failure

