Acta Anaesthesiol Scand. 2015;59(7):912-920. doi:10.1111/aas.12525

Appendices

Appendix 1: Standard operating procedure for anesthesia to major abdominal laparotomy and laparoscopic surgery at Hvidovre Hospital

LOP nr. 102

Instruks vedrørende anæstesi til større abdominalkirurgisk laparoskopi og laparotomi

Område:

Denne LOP dækker anæstesi til:

- Colon og rectum resectioner både åbne og laparoskopiske
- Ventrikel og tyndtarmskirurgi ikke dækket i andre SOP
- Tilbagelægning af end-stomier
- Større ventralhernieoperationer (jvf LOP 104)
- Større abdominalkirurgiske indgreb der ikke er dækket af andre LOP

Denne LOP dækker *IKKE* akut abdominalkirurgi og elektive indgreb på ventrikel og oesophagus, til hvilke der findes separate SOP.

Præmedicin:

Al vanlig medicin fraset marevan, clopidogrel, magnyl og antidiabetisk medicin.

Anæstesimetode:

Som standard anvendes generel anæstesi med intubation og epidural anæstesi anlagt præoperativt.

- Luftvejsvurdering og håndtering foretages jvf SOP 272: luftvejshåndtering af patienter i generel anæstesi
- Alle patienter skal have Bair-hugger på højeste indstilling.
- Ved laparoskopi: **Ventrikelsonde** efter intubationen
- Patient skal have mindst én arm tilgængelig for anæstesen. Hvis begge arme på helt særlig indikation lægges ind til siden, skal der etableres PVK eller CVK på hals.
- Mindst to iv adgange, hvor den sidste kan anlægges efter induktion.
- **Obs** risiko for tryk fra og på iv adgange, polstres evt med vaskeklude.
- Foreslå kirurg "normalt leje" x 1/time ved Trendelenburg

HUSK antibiotika efter skema

Anæsthesimetode:

Epidural

Test: Lidokain 2% m.adr., 3 ml

Bolus: Marcain 0.5 %, 5+5 ml med fem minutters mellemrum.

Epi-morfin: 2 mg (< 70 år); 1 mg (>70 år)
Ved tidligere opkastning pga. morfin - ingen bolus

Øvre (ventrikel til colon transversum):
Epidural anlægges på **T7-8** niveau

Nedre (venstre colon til rectum):
Epidural anlægges **T9-10** niveau

Ved epidural anlæggelse kan analgeseres med Remifentanyl 0.1-0.2 mikrog/kg/min

Vedligeholdelse:

- Epiduralpumpe 4 ml/time "standardblanding".
- Marcain 0,25 %, 5 ml/2.time og ved kirurgiafslutning.
- Tidligere PONV pga. morfin, skift til Sufenta 1 mcg/ml i pumpen.

Generel

Induktion:

- Propofol 1.0-2.0 mg/kg
- Remifentanyl 5-6 mikrog/kg
- Dexamethason 8 mg
- Start infusion

Vedligeholdelse:

- Propofol 3-5 mg/kg/time
- Remifentanyl 0.5 mikrog/kg/min

10 minutter før kirurgiafslutning:

- Toradol 30 mg i.v. (ikke ved rectum anastomoser)

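### The risk section says the study changes no treatment, but the Intervention section withholds the Hvidovre procedure's dexamethasone 8 mg for a study reason, and the risk section does not list this

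*Combined protocol and SAP*

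**What the plan says.** Two sentences open the section Risks, harms and inconveniences: "Patients will receive the standard care at the respective hospital", and then "The study does not influence any treatment or intervention related to the hospitalization". Two headed items follow, one on peripheral blood sampling and one on the QoR-15 questionnaire. No drug is mentioned.

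The Intervention section says that Hvidovre participants are anesthetized by the hospital's standard operating procedure "with the exception that no dexamethasone is administered as it could modulate the immune response". It adds: "Patients will receive 4 mg ondansetron at the end of anesthesia".

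Appendix 1 reproduces the standard procedure. Its induction list for general anesthesia includes "Dexamethason 8 mg". Its list for ten minutes before the end of surgery includes Zofran (ondansetron) 4 mg intravenously.

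**The concern.** One part of the protocol removes a drug from the standard procedure for a scientific reason. Another part says that the study changes no treatment. Both cannot be true of the Hvidovre cohort.

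The matter is participant protection, not a statistical result. The section on consent guidelines says that an investigator will explain risks, harms and inconveniences to patients, and the protocol section that bears this heading is the one that denies any change in care. Ethical considerations makes approval by the regional committee mandatory. A reader who goes to the risk section to learn what participation changes would conclude that it adds only blood sampling and a questionnaire.

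**Working it through.** No power or alpha figure bears on this point, and the plan states no figure to reproduce. The check is a comparison of sections, with simple arithmetic on doses and numbers.

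**1. Does the study change a drug?**

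| Drug | Standard procedure (Appendix 1) | Study (Intervention) | Difference |
|---|---|---|---|
| Dexamethasone at induction | 8 mg | 0 mg | 0 − 8 = −8 mg |
| Ondansetron at end of anesthesia | 4 mg | 4 mg | 4 − 4 = 0 mg |

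The dexamethasone entry carries no condition. Elsewhere the same procedure does state conditions where they apply: epidural morphine depends on age, and Toradol is not given with rectal anastomoses. The plain reading is that dexamethasone is part of the standard induction. The ondansetron line adds nothing to the standard procedure, so it cannot be read as compensation for the omitted drug.

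**2. Is the omission a condition of the study or a clinician's choice?** The stated reason is possible modulation of the immune response, which is what the study measures. No patient-care reason is given. The withdrawal criteria also allow a participant to be withdrawn when the described anesthesia intervention is not followed, and the omission is part of that description. It is a study requirement.

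**3. Whom does it affect?** Every Hvidovre participant. The Sample size section expects 36 inclusions to obtain 30 evaluable patients with 10–20% withdrawal. From those inputs:

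- 10% withdrawal: 30 / 0.90 = 33.3, rounded up to 34
- 20% withdrawal: 30 / 0.80 = 37.5, rounded up to 38

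The stated 36 lies within 34 to 38. The Zealand patients contribute electronic data only, so the statement that this study does not influence treatment is not contradicted for them.

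**4. Does the risk section list it?** Items listed: 2 (blood sampling, QoR-15). Treatment changes listed: 0. Treatment changes imposed by the protocol: at least 1.

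**5. Does other text reconcile the two statements?** None was found. The Intervention section itself calls the omission an exception to the standard procedure, so standard care cannot be taken to include it.

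**The case against.** The strongest defense is that nothing is hidden. The Intervention section states the omission and its reason, and the full standard procedure is appended, so an ethics committee that reads the whole protocol can see it. That stands, and it keeps the severity down. It does not correct a categorical denial in the section that deals with risk.

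It is also fair to say that no harm is documented. The protocol does not say why the standard procedure includes dexamethasone, what follows from leaving it out, or how often it is given in practice. The documents therefore support disclosing the change, but not naming a particular missing harm.

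A reader might infer more than this. Four such readings are not supported:

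- *Patients or the committee were misinformed.* The consent pages are not available, and the omission may have been explained to both. Only the protocol text can be faulted.
- *The comparison with Zealand is biased.* The protocol does not say whether Zealand patients received dexamethasone, so no such bias can be shown from it.
- *The epidural regimen is a second departure.* The Intervention section says that "continuous infusion of bupivacaine and sufentanyl will be used to maintain the epidural analgesic effect". Appendix 1 sets "Epiduralpumpe 4 ml/time" of a standard mixture and mentions sufentanil as a switch: "Tidligere PONV pga. morfin, skift til Sufenta 1 mcg/ml i pumpen". The composition of the standard mixture is not given, so a difference cannot be established, and the Intervention section declares only one exception.
- *The analysis mislabels the exposure.* Data analysis names total intravenous anesthesia with epidural and does not mention dexamethasone. The Population section, however, defines the study group by the intervention already described, which includes the omission. The shorter label is shorthand.

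**Conclusion.** The concern holds as an internal inconsistency of minor to moderate weight. The risk section claims a property that the design does not have, and it leaves out the one treatment change that the protocol declares.

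Its size is dexamethasone 8 mg omitted by protocol for each of about 36 Hvidovre participants. This assumes that the appended procedure describes what these patients would otherwise have received. If actual use outside the study is lower, fewer patients are affected in practice, but the contradiction in the text remains. No bias, size of harm, or effect on the sample size or the primary analysis is claimed.

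**What to change.** Keep the omission; its reason is stated and fits the aim of the study. Then:

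1. Replace the two opening sentences of the risk section with one that covers both hospitals, for example: *Care follows usual practice at each hospital, except that at Hvidovre dexamethasone 8 mg at induction is omitted for study reasons.*
2. Add the omission as a third listed item in that section, with its foreseeable consequences as judged by the responsible anesthesiologist.
3. Make sure that the patient information and the ethics text say the same.

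The cost is one rewritten statement, one added risk item and a consistency check. Design, sample size and analysis stay as they are. There are two downsides. The study can no longer be described as having no influence on care. And if the change counts as an important modification, Ethical considerations requires it to be approved by the committee before it is implemented.
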